Participants will have access to audio recordings of the protocol (pre-recorded by [name], study PI) via secure streaming online that will work on any computer or mobile device with internet access. Patients will be assigned a new hypnotherapy session to listen to every 2 weeks and these will become automatically available in the correct sequence. Each hypnotherapy session

will be approximately 30 mins in length. The hypnotherapy sessions are verbally guided exercises, similar to guided meditation. The hypnotherapy sessions encourage patients to enter a state of focused mental attention and deep physical relaxation during which images and verbal suggestions are used to positively influence emotional and physical symptoms. The session developed for this intervention will specifically focus on mechanisms that contribute to functional dyspepsia symptoms, such as impaired relaxation of the stomach and pain sensitivity. For example, after facilitating a deeply relaxed state patients will be asked to visualize drinking a cool liquid that has a therapeutic effect on the stomach (i.e., decreases pain, allows the stomach to stretch and make room for food). Each of the 7 sessions will utilize different imagery.

Patients will be instructed to practice a shorter 10-12 minute audio recording 5 times per week in between the longer sessions. After the 12-week treatment course is completed, patients will be able to continue to listen to the shorter home hypnosis recordings as often as they choose for up to one year.

The web page will give patients pop-up notices to encourage them to increase their frequency of practice if their weekly frequency drops below the recommended 5 days of home practice. Patients who do not log into the online system to complete a hypnosis exercise for 7 consecutive days will be contacted by the study coordinator to discuss whether the patient is interested in continuing with the trial.

Additionally, patients will receive phone or MyLoyola messaging (patient preference) from a study coordinator every 2 weeks to encourage adherence and troubleshoot any difficulty using the recordings and assess any adverse effects. If they have any difficulties or discomforts associated with the self-administered hypnosis intervention during the trial, they will have an opportunity to talk with [name] on the phone to resolve these.

The Study Website

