- **The Rome IV Dyspepsia Module** will be administered at baseline to confirm diagnosis of functional dyspepsia. This self-report questionnaire is used to diagnosis functional GI disorders based on Rome IV criteria.²
- **The Patient Assessment of Upper Gastrointestinal Symptom Severity Index (PAGI-SYM)** will be administered to assess symptom severity. The PAGI-SYM measures 20 dyspeptic symptoms on a 6-point Likert scale, 0 (no complaints) – 5 (severe complaints), subdivided into six subscales: heartburn/regurgitation, nausea/vomiting, postprandial fullness/early satiety, bloating, upper abdominal pain, and lower abdominal pain. The measure has demonstrated good reliability and validity for measuring symptom severity in patients with functional dyspepsia.²⁵
- **The Short Form Napean Dyspepsia Index (NDI-SF)** is a 10-item disease specific quality of life questionnaire developed for clinical trials in functional dyspepsia. The NDI has been established to have excellent psychometric properties²⁶ and responsiveness to treatment change has been confirmed²⁷ and the 10-item short form is recommended for use in clinical trials.²⁸
- **Visceral Anxiety (VSI):** The VSI is a 15-item questionnaire that will be used to assess gastrointestinal specific anxiety²⁹. This measure assesses fears of GI symptoms and is a predictor of symptom severity in patients with functional GI disorders. The VSI uses a 6 point likert scale response format with total scores ranging from 0 to 75; higher scores indicate more severe symptom-related anxiety.
- **The Brief Symptom Inventory (BSI)** will be used to assess depression, anxiety, and somatization.³⁰ The BSI is an 18-item questionnaire using a 5-point likert scale with scores ranging from 0 to 68; higher scores indicate higher levels of distress.
- **Thought Impact Scale- Short Form (TIS-SF).** This 17-item questionnaire is a short-form version of the Thought Impact Scale, a newly validated measure designed to predict clinical response to hypnosis treatment. The TIS-SF will be administered at baseline only to assess whether the traits that it measures (i.e., subconscious

connectedness) correlates with the degree of FD symptom improvement in the study.³¹

- **Adherence to Hypnosis Practice:** Use of hypnosis sessions will be recorded automatically by the audio player page on the treatment web page, to track frequency of home practice of hypnotherapy by the HYP intervention participants.

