- **Health care utilization:** Patients will be asked at baseline, end of treatment and at 3-month follow-up to report the number of outpatient visits and procedures they have had within the last 3 months related to their functional dyspepsia symptoms. They will also be asked to report any changes in medications they have taken related to their functional dyspepsia symptoms.
- **Satisfaction with the treatment and global outcome:** At the end of treatment only (12 weeks), patients will be asked additional two questions to assess how satisfied they were overall with their assigned treatment (on a 7-point scale from "Extremely dissatisfied" to "Extremely satisfied") and how they feel their FD symptoms have changed overall since before the start of treatment (from "very much worse" to "very much improved").
- **Satisfaction with web-based platform.** At the end of treatment only (12 weeks), patients will be asked an open-ended question to obtain feedback on their experience using the web-based platform for treatment ("Please describe any difficulties you had using the web interface and/or suggestions on ways we could improve the website.").

VII. Safety Monitoring Plan

a. Definition of adverse events, serious adverse events

- Participant risks in this study are minimal. We will screen individuals prior to enrolling them in the study and any patients with psychological comorbidities that increase risk of adverse events associated with hypnotherapy (e.g., post-traumatic stress disorder) will be ineligible to participate. However, even with careful screening, it is possible that participants may experience emotional discomfort or increased anxiety as a result of participating in the hypnotherapy treatment or completing study questionnaires. We will encourage participants to contact us should they experience discomfort or emotional distress during course of treatment. [name], study PI and licensed clinical psychologist, will be available to discuss these concerns and further assess the patients psychological functioning and

discontinue treatment if necessary. We will also provide referrals for counseling outside of the study if needed.

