- We will take steps to reduce the risk of discomfort associated with answering questions on assessment measures related to psychological functioning by allowing participants to leave blank any questions that may make them uncomfortable. The participant will be reminded that s/he has the option of stopping treatment and can refuse to answer any questions s/he is asked that s/he finds distressing. However, the study team shall determine if the extent of refusal may warrant removal of the participant from the research study to ensure complete and accurate data collection.

b. What procedures will be used to monitor subject safety?

- Participants will be given contact information for study personnel and encouraged to reach out if they experience an increase in psychological distress related to the treatment. Participants will be told that they are welcome to withdraw from the study at any time.
- We plan to use an electronic platform for this study to deliver the hypnotherapy sessions as well as to conduct all patient evaluations online. It is same technology as [name] has used successfully for online data collection in multiple NIH-funded RCT clinical trials. All study questionnaires will be administered electronically in the password-protected online portal via highly secure Qualtrics Research Suite software, and all questionnaire data will moreover be collected in a fully de-identified manner that neither obtains nor stores online any information that can reveal the personal identity of participants. This is accomplished by associating patient responses only with their randomly assigned study ID numbers.
- The online hypnotherapy program is considered an investigational device under the Food and Drug Administration (FDA) regulations and is categorized as a nonsignificant risk device.
- Patient names will be keyed into unique subject code and the keyed file will be kept separate from the data file to ensure patient confidentiality. Data downloads will be stored in a secure study folder in HIPAA-compliant LUMC file server space, with study folder access restricted to IRB-approved study personnel. Any non-electronic study data will be stored in locked filing cabinets, accessible only by IRB-approved study personnel. Data will be stored for 7 years after study completion per IRB policy.

c. Who (list names) will identify, document, and report adverse events?

[name], study PI

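### Section VII.b invites reports only of psychological distress linked to treatment, so emergency visits, admissions or new organic disease not blamed on hypnosis may go unrecorded, above all after week 12

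*Combined protocol and SAP*

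**What the plan says.** Safety and health-event collection is spread over several sections of the combined protocol and SAP.

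- **Section VII.b (monitoring procedures).** Participants receive contact details and are "encouraged to reach out if they experience an increase in psychological distress related to the treatment".
- **Section VII.a (adverse event definitions).** The text under this heading describes emotional discomfort and anxiety as possible harms and then says: "We will encourage participants to contact us should they experience discomfort or emotional distress during course of treatment". It defines neither adverse event nor serious adverse event.
- **Section VI.c (Study Intervention).** "patients will receive phone or MyLoyola messaging (patient preference) from a study coordinator every 2 weeks to encourage adherence", and the same sentence adds that the contact is to "troubleshoot any difficulty using the recordings and assess any adverse effects". The next sentence offers a phone call with the principal investigator on a condition: "If they have any difficulties or discomforts associated with the self-administered hypnosis intervention during the trial".
- **Section VI.d (Health care utilization).** At baseline, end of treatment and 3-month follow-up, participants "report the number of outpatient visits and procedures they have had within the last 3 months related to their functional dyspepsia symptoms". Then: "They will also be asked to report any changes in medications they have taken related to their functional dyspepsia symptoms".
- **Section VI.d (symptom measures).** "The PAGI-SYM measures 20 dyspeptic symptoms on a 6-point Likert scale". It is collected at weeks 0, 6 and 12 and at 3-month follow-up. A global change item at week 12 has a scale that extends to marked worsening.
- **Section VII.c.** The principal investigator identifies, documents and reports adverse events.

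**The concern.** The monitoring section is where staff will look for what to ask participants to report. Its wording sets two conditions: the problem is psychological, and it is related to the treatment. The second asks participants to judge cause before they make contact. Yet the participants have a gastrointestinal disorder, organic gastrointestinal disease is an exclusion, and after screening they are followed mainly through a web portal. The events that would matter most for safety, such as an admission or an organic diagnosis that emerges during follow-up, are ones a participant would have little reason to blame on an audio recording.

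At stake is how far the pilot's safety record can be relied on. The data are meant to inform a later randomized trial, and the protocol treats the program as an investigational device. If unattributed or physical events are not sought consistently, a record with few or no events is hard to interpret.

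**Working it through.** The plan states no figure on this point, so none can be reproduced. The check sets each described route beside the others.

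| Route | Started by | Scope | Must be tied to hypnosis? | Period described |
|---|---|---|---|---|
| VII.b invitation | Participant | Psychological distress | Yes | None stated |
| VII.a invitation | Participant | Discomfort or distress | No | Treatment course |
| VI.c coordinator contact | Staff, every 2 weeks | Any adverse effects (undefined) | Unclear | Described with treatment; no end stated |
| VI.c call with principal investigator | Participant | Difficulties with the intervention | Yes | During the trial |
| VI.d utilization item | Questionnaire | FD outpatient visits, procedures, medication changes | No, but tied to FD | Baseline, week 12, 3 months |
| VI.d PAGI-SYM | Questionnaire | 20 symptoms | No | Weeks 0, 6, 12 and 3 months |
| VI.d global change item | Questionnaire | Overall FD change | No | Week 12 only |

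**Time covered.** Treatment of 12 weeks plus follow-up of 12 weeks gives 24 weeks. The 2-weekly contacts are described with the treatment course, and nothing says that they continue. That leaves 12/24, or half, of the described period without a stated staff-initiated safety contact. Section VI.c lets participants keep using the shorter recordings after the course for up to one year, so exposure can continue. One phone contact may fall after week 12. Seven sessions at 2-week intervals span (7 − 1) × 2 = 12 weeks, and the optional interview takes place within one month of the last session. Its stated purpose is experience and satisfaction, not safety.

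**Three test events, none blamed on hypnosis.**

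1. *Emergency visit or admission.* It does not meet the VII.b conditions. The utilization item, as described, asks for outpatient visits and procedures and only for FD-related ones. During treatment, capture depends on how coordinator and participant read adverse effects. After week 12, no described question asks for it.
2. *Newly found organic disease.* It does not meet the VII.b conditions either. An investigation for dyspepsia might add to the procedure count, but the item as described asks how many, not what was found.
3. *Worsening gastrointestinal symptoms.* These are measured by the PAGI-SYM and, at week 12, by the global item. No stated rule sends a worse score to adverse-event review, so the worsening would be in the outcome data without necessarily being recorded as an event.

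**The case against.** A reader who starts from Section VII.b might infer that safety reporting as a whole is limited to distress the participant attributes to hypnosis, and that an event is recorded only if the participant volunteers it and blames the treatment. The documents do not support that. Section VI.c has staff contact every participant every 2 weeks, and assessing adverse effects is a separate purpose of that contact, not confined to psychological events. Section VII.a invites contact without requiring attribution. Section VII.b is an invitation to participants, not a recording rule, and Section VII.c gives identification and documentation to the principal investigator.

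A reader might also infer that worsening symptoms go unseen. They do not, because they are collected as outcomes. Nor can it be said that admissions are never asked about: Section VI.d refers to Appendix D for the full survey items, and that appendix was not available. It can also be argued that a 23-patient feasibility pilot of a device classed as nonsignificant risk, with no safety endpoint, does not need all-cause counts.

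All of this stands against the stronger readings. It does not remove the narrower point. The sections give different scopes, the term that would settle them is undefined, no admission or emergency item is described, and no safety contact is stated after week 12. Small size and low expected risk lower the urgency, but the remedy is also small.

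**Conclusion.** The point holds as a gap in scope and timing. The plan does seek adverse effects during treatment, but Section VII.b is narrower than Sections VI.c and VII.a. An emergency visit, an admission or a new organic diagnosis not attributed to hypnosis may therefore not be captured as an event, and the gap is widest in the 12 weeks after treatment.

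Its size can be stated only as coverage: half of the 24 weeks has no described staff-initiated safety contact. A probability of missed events would need an event rate and a capture rate. The documents give neither, and any capture rate would have to allow for the 2-weekly contact.

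The conclusion assumes that Appendix D contains no all-cause admission or emergency item and that the 2-weekly contacts end with treatment. If either assumption is wrong, the point shrinks accordingly, but the mismatch between sections remains. The unanswered question on frequency of safety review in Section VII.d is not counted, because the answer may have been removed before publication. The change is worth making as an inexpensive improvement; no endpoint or sample size is affected.

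**What to change.** First check Appendix D for an admission or emergency-care item. Then:

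1. Reconcile Sections VII.a and VII.b with Section VI.c. Ask participants to report any new or worsening psychological, gastrointestinal or other physical problem, whatever they think caused it.
2. Put that same open question to every participant at the existing 2-weekly contacts, and add it to the 3-month follow-up questionnaire. The principal investigator, not the participant, judges relatedness. Because the question names gastrointestinal problems, worsening reaches the investigator directly and no score threshold has to be invented.
3. Add two counts, emergency visits and hospital admissions for any reason, to the utilization question at end of treatment and at 3-month follow-up. The item already looks back 3 months, so these two time points together cover treatment and follow-up.

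The cost is a wording change in two subsections, one standard question at contacts and in a questionnaire that already exist, and two extra fields in an online form. The downside is that more unrelated events will have to be logged and assessed, which is manageable with 23 participants.

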A published pilot study of hypnotherapy for IBS delivered entirely through audio recordings by co-investigator [name] and his colleagues serves as a model for the hypnosis treatment in this FD trial¹⁹. That study found that IBS patients who completed a seven-session self-administered audio home hypnosis treatment course were twice as likely (53% vs 26%) to have a reduction in their gastrointestinal symptoms by half or more at 6 months compared to matched control patients of the same age and sex and equal symptom severity who only received standard medical care. We will script the audio-recorded hypnosis protocol in the present trial to be similar in structure and therapy approach, as IBS and functional dyspepsia are both functional GI disorders and have many similarities and a high degree of overlap (the intervention tested in the prior hypnosis trial by Calvert et al., that showed high success in FD treatment, also utilized modified IBS hypnosis treatment for that purpose).

III. Study Aims

The purpose of this pilot study is to develop and test a hypnotherapy (HYP) treatment program for functional dyspepsia (FD) that can be self-administered using on-line audio recordings. We hypothesize that patients will be receptive to the self-administered treatment design and willing to participate and complete the 12-week treatment program.

Furthermore, we expect that patients will experience a significant reduction in FD symptoms following the intervention. Our specific aims include:

Aim 1: Feasibility and Acceptability of Treatment

The study will assess whether patients with FD will be willing to participate in the on-line treatment program and the majority of patients enrolled in the study will complete the 12 week program, utilize the materials sufficiently, and report average to above average satisfaction with treatment.

Aim 2: Treatment Effectiveness

The primary endpoint for Aim 2 is significant reduction in pre- to post- treatment FD symptom scores. Secondary endpoints include significant improvements in pre- to post-treatment score on psychological indices (e.g., anxiety) and disease-specific quality of life.

IV. Administrative Organization

All administrative activities related to the study will take place within the Division of Gastroenterology and Nutrition at Loyola University Medical Center (LUMC).

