Administrative offices for the division are located in the Fahey Building on the LUMC campus where office furniture, file cabinets, and use of essential equipment (e.g., copier, fax, phone, computer) will be provided.

V. Study Design

a. Experimental design of the study:

This is a non-randomized observational study designed to provide preliminary data on the feasibility and effectiveness of a self-administered HYP treatment for FD.

b. Study population general description

Eligible patients will be referred by Gastroenterologists within the Digestive Health Program at Loyola University Medical Center and will have received a diagnosis of functional dyspepsia. Additionally, any patients with functional dyspepsia referred by outside providers to [name] GI Behavioral Medicine Service at LUMC will be made aware of the study.

c. Sample size determination and power analyses

We will enroll 23 adults with FD from the Loyola University Medical Center outpatient gastroenterology practices, with the aim of assessing feasibility and acceptability of HYP treatment using on-line audio recordings. Sample size was determined for aim 1 of the study. Allowing for up to 20% drop-out and having at least 16 patients complete the study through the end of treatment (where the primary endpoint will be measured) will provide sufficient participant feedback on the web interface as well as the pilot data needed to power a future randomized controlled trial.

d. Study outcomes/endpoints

The primary endpoint for this study will be FD symptom scores. Secondary endpoints will be disease-specific quality of life, psychological indices, and patient satisfaction.

VI. Study Procedures

a. Subject selection procedures:

We will enroll 23 adults with FD.

Inclusion criteria

- (1) Diagnosis of functional dyspepsia by a gastroenterologist
- (2) Meeting ROME IV diagnostic criteria for functional dyspepsia
- (3) At least 18 yrs of age (no upper age limit)
- (4) Able to give informed consent
- (5) English speaking
- (6) Have daily personal access to the Internet via laptop or desktop computer, tablet or a smartphone.

Exclusion criteria

- (1) Concomitant organic gastrointestinal disease
- (2) Diagnosed or presenting with serious mental illness (e.g., eating disorder, schizophrenia, psychosis, obsessive-compulsive disorder, post-traumatic stress disorder, or a dissociative disorder)

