4. What happens with screen failures (including any data gathered during screening)? Data will not be collected on patients that are screened as ineligible for the study. However, these patients will be provided with recommendations for alternative treatment options by their gastroenterologist (medications, diet changes), alternative psychological treatments within the Loyola GI behavioral medicine program, or a referral to an outside provider depending on patients' needs.

- b. Randomization procedures (if applicable): N/A
- c. Study Intervention

Patients will be given access to a password protected website containing HYP treatment materials. They will be instructed by the study coordinator to log on to the website within 1 week to complete baseline assessment questionnaires and watch an instructional video. This video will be pre-recorded by [name] (study PI). The content of the video will include educational information about the patient's diagnosis, provide rationale for hypnotherapy treatment, set expectations for treatment, and dispel myths about hypnotherapy. The video will also provide instructions on implementing the treatment protocol, including guidance on selecting a time and place to practice hypnotherapy and recommendations for weekly practice with audio recordings (5x per week). See Appendix B for a full script of this introductory video (video will be filmed after we receive IRB approval).

We have developed a 7- session, hypnosis protocol for functional dyspepsia that is similar to an evidence-based protocol for irritable bowel syndrome developed by co-investigator [name], which has been found to be efficacious in 7 published studies²⁴. This protocol was jointly scripted by Drs. [name] and [name], and is based on the successful scripted therapy approach for IBS, with appropriate adaptations. See Appendix C for the full scripted protocol of the 7 hypnotherapy sessions as well as the shorter practice session that will be audio recorded. This will be the full content of the audio recordings, subject to final minor edits and polishing, prior to recording which will be scheduled after we receive IRB approval.

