d. What is the frequency for review of summarized safety information and who will perform the review (e.g., safety monitoring board)?

- e. What are the stopping rules with regard to efficacy and safety?
Patients are free to withdraw from treatment at any time.

VIII. Analysis Plan

Aim 1: Feasibility and Acceptability of Treatment. Methods: Eligible and enrolled patients will be followed to assess the percentage who log-in to the web interface, utilize the materials sufficiently, complete the 12 week program, and report at least average satisfaction with treatment. We will present descriptive statistics to report treatment satisfaction and patient-reported global ratings of outcome, both of which will only be assessed at 12 weeks. Feasibility will be calculated as the proportion of participants who complete the FD HYP treatment program in comparison to those who drop out before treatment is completed. We expect that the proportion of participants who are retained will be 80%, demonstrating feasibility of recruitment and retention. Treatment satisfaction will be calculated as the proportion of patients who started treatment (dropouts included) who report that they are satisfied with the treatment (i.e., endorse the response either options “Somewhat satisfied”, “Very satisfied” or “Extremely satisfied” on the 7-point treatment satisfaction measure). We expect that the majority of patients will report satisfaction with the treatment. Sample size justification: For the aim of retention, a sample size of $n=23$ achieves 92.8% power for a one-sided exact test for a proportion retained of 80%. This test assumes the null hypothesis proportion retained is 50%, and we will reject the null hypothesis and conclude retention is acceptable should at least $n=16$ (69.6%) be retained. Similarly, for the aim of satisfaction, a sample size of 21 achieves 90.5% power for a one-sided exact test for a proportion satisfied of 50%. This assumes 20% satisfaction under the null hypothesis, and we will reject the null hypothesis if at least 39% of the sample report they are satisfied with treatment. Both tests were targeted at an $\alpha=0.05$ significance level.

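### The satisfaction test counts only patients who started treatment, while Aim 1 is stated for enrolled patients; the effect is modest, but the denominator and cut-off need to be fixed at 9 of 23

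*Combined protocol and SAP*

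**What the plan says.** Section III, Aim 1, sets its expectation for enrolled patients: the "majority of patients enrolled in the study will complete the 12 week program, utilize the materials sufficiently, and report average to above average satisfaction". Section V.c fixes enrolment at 23.

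Section VIII, Aim 1, opens on the same base ("Eligible and enrolled patients will be followed to assess the percentage who log-in to the web interface") and lists satisfaction among the things to be assessed in that group. The calculation rule a few sentences later uses a different group: "Treatment satisfaction will be calculated as the proportion of patients who started treatment (dropouts included"). Dropouts after starting stay in; enrolled patients who never start do not.

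The same section sizes retention on n = 23, with success at 16 or more. For satisfaction, "a sample size of 21 achieves 90.5% power for a one-sided exact test for a proportion satisfied of 50" per cent; "This assumes 20% satisfaction under the null hypothesis", and the null is rejected if at least 39% of the sample are satisfied. The plan defines neither the sample nor what counts as starting treatment, and it does not explain the 21.

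**The concern.** One test has three possible bases: 23 enrolled, 21 in the power statement, and however many start. In this design, enrolling and starting are separate events. After the screening visit patients receive access details by e-mail and must then "log on to the website within 1 week to complete baseline assessment questionnaires and watch an instructional video" before self-administered sessions begin. Aim 1 asks in part whether patients are willing to take part in an online programme. Someone who consents and never begins bears directly on that question, yet drops out of the acceptability test while still counting in the retention base.

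At stake is whether the satisfaction result answers Aim 1 as written, and whether the number of satisfied patients needed for success depends on how many enrolled patients fail to start.

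**Working it through.** **Inputs.** From Section VIII: null 20%, alternative 50%, one-sided exact test at 0.05, n = 21, power 90.5%, cut-off 39%; for retention n = 23, null 50%, alternative 80%, cut-off 16, power 92.8%. From Section V.c: enrolment 23, drop-out up to 20%, at least 16 completers. The number of non-starters is not given. It is an assumption here, shown from 0 to 7, since 7 is the most that still allows 16 completers.

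**Formula.** For a rule of r or more out of n, the chance of success is P(X ≥ r) with X ~ Binomial(n, p). Alpha uses the null p and power the alternative p.

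**Reproducing the plan's figures.**
- Retention, 16 of 23: alpha 0.0466, power 0.9285. This matches 92.8%.
- Satisfaction, 8 of 21: alpha 0.0431, power 0.9054. This matches 90.5%.

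But 8/21 = 38.1%, which is below 39%. Read literally at n = 21, the rule needs 0.39 × 21 = 8.19, so 9 patients, with alpha 0.0144 and power 0.808. The 39% figure does fit 9/23 = 39.1%.

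**Effect of non-starters.** With m starters, the literal rule needs 0.39 × m rounded up to a whole patient.

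| Non-starters | Starters m | 0.39 × m | Needed | % of starters | % of 23 | Alpha among starters |
|---|---|---|---|---|---|---|
| 0 | 23 | 8.97 | 9 | 39.1 | 39.1 | 0.0273 |
| 1 | 22 | 8.58 | 9 | 40.9 | 39.1 | 0.0201 |
| 2 | 21 | 8.19 | 9 | 42.9 | 39.1 | 0.0144 |
| 3 | 20 | 7.80 | 8 | 40.0 | 34.8 | 0.0321 |
| 4 | 19 | 7.41 | 8 | 42.1 | 34.8 | 0.0233 |
| 5 | 18 | 7.02 | 8 | 44.4 | 34.8 | 0.0163 |
| 6 | 17 | 6.63 | 7 | 41.2 | 30.4 | 0.0377 |
| 7 | 16 | 6.24 | 7 | 43.8 | 30.4 | 0.0267 |

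If the exact 0.05 critical value is used in place of the literal 39%, the only change in this range is at 21 starters, where 8 suffices.

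**Drop-out allowance as a yardstick.** 0.20 × 23 = 4.6, so at most 4 whole patients. Within it the minimum is 9 or 8. Five non-starters (21.7%) already lie just above it; six or seven (26.1% or 30.4%) lie clearly above it.

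**Same counts on all 23 enrolled.**
- 9 of 23: alpha 0.0273, power 0.895 at 50%.
- 8 of 23: one-sided p = 0.0715, so the 20% null is not rejected.
- 7 of 23: one-sided p = 0.160, not rejected.

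**The case against.** The starter denominator is stated openly and can be defended. The question asks about satisfaction with the treatment, and someone who never heard a session has no experience to rate. Keeping later dropouts in already prevents a completers-only result. Non-starters also show up elsewhere in Aim 1: in the log-in percentage and in retention.

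Part of this stands: nothing is hidden, and other measures do register non-starters. But the log-in percentage is descriptive and does not enter the satisfaction decision. The argument about rating is also weakened by the plan itself. Satisfaction is asked only at 12 weeks (Section VI.d), so a dropout who never answers stays in the denominator and cannot enter the numerator. Treating non-starters the same way extends what the plan already does.

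A reader might infer more than the documents support:

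- *That success with 7 of 23 is the expected case.* It needs 6 or 7 non-starters, above the 20% allowance. With 6, retention would also require at least 16 of 17 starters to complete. If 80% of starters complete (an assumption), that has probability 0.118.
- *That every non-starter makes success easier.* The observed percentage can only rise, but under the literal rule the first two non-starters leave the requirement at 9.
- *That type I error is inflated.* Among starters, alpha stays below 0.05 in every row of the table. The shortfall concerns the enrolled population only.
- *That changing the denominator makes the test address a majority.* It does not. Even 9/23 is 39.1%, and the low bar comes mainly from the 20% null.

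**Conclusion.** The mismatch is real. Aim 1 and the opening of its methods name enrolled patients; the calculation rule names starters. The consequence is modest and conditional: no change in the requirement with 0 to 2 non-starters, one patient fewer with 3 to 5, and two fewer only with 6 or 7. The case that matters is 8 satisfied patients with 3 or 4 non-starters, which is inside the drop-out allowance: it passes as written, yet does not reject the 20% null among the 23 enrolled (p = 0.072).

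This rests on the literal 39% cut-off applied to starters, on starting meaning something later than enrolment, and on an unknown number of non-starters. If the sample in the 39% rule was meant to be all 23, the cut-off is already 9 and only the definition of the proportion needs correcting. The n = 21 statement is inconsistent with the 39% cut-off on any reading. The change is worth making because it is cheap and aligns the test with its aim, not because the present test is invalid.

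**What to change.** In Section VIII, Aim 1:

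1. Define the satisfaction proportion on all 23 enrolled patients. Count non-starters, and dropouts without a 12-week answer, as not satisfied.
2. State one integer cut-off: at least 9 of 23 (39.1%), with exact one-sided alpha 2.7% at 20% and power 89.5% at 50%.
3. Delete the n = 21 and 90.5% statement, which this replaces.
4. Define starting treatment, and report the number of non-starters and the proportion satisfied among starters as descriptive figures.

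The cost is wording and a revised sample-size sentence; no extra patients or data are needed. The reported satisfaction percentage will be somewhat lower if anyone fails to start, and the stated power falls from 90.5% to 89.5%.
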